### **3.6.5.7 Chest X-ray**

Posterior-anterior and lateral chest X-rays (or chest radiographs in accordance with local requirements) should be obtained at Screening and reviewed by the Investigator or designee. At Screening, if chest radiographs taken within the past 3 months show no clinically significant abnormality, and there are no signs or symptoms suggestive of pulmonary disease that would exclude the patient from the study, then a chest radiograph does not need to be repeated.

### **3.6.6 End of Study**

All patients will be followed up for up to 52 weeks from the start date of the first course of study drug. The patients who discontinue the study treatment attend all visits until Week 52 in order to address any safety concerns, to record the concomitant medications, and to measure drug level, CD19+ B cell count immunogenicity and efficacy (if applicable).

### **3.6.7 Data Safety Monitoring Board**

An independent Data Safety Monitoring Board (DSMB) will be assigned for this study. The DSMB will review available study data at pre-specified time points as outlined in the DSMB charter. The details of the DSMB roles and responsibilities and details of the review process will be outlined in the DSMB Charter.

## **3.7 Stopping Rules, Discontinuation Criteria, and Procedures**

### **3.7.1 Entire Study or Treatment Arms**

If the Sponsor decides to terminate or suspend the study for safety or unanticipated other reasons, the Sponsor will promptly notify the Investigators, Sub-investigators, Institutional Review Boards/Independent Ethics Committees (IRBs/IECs), and Regulatory Authorities as required by the applicable regulatory requirements.

### **3.7.2 Individual Study Center**

The Sponsor, IRB/IEC and/or Regulatory Authorities have the right to close an individual study center at any time. In case of premature termination of an individual study center, the Sponsor, Investigator, participating study patients, IRB/EC and Regulatory Authorities should be informed as described in ICH-GCP and according to other applicable regulatory requirements.

Prior to closure of the study center, the Investigator or institution must assure appropriate therapy and follow-up for the patients.

The Sponsor may decide to close an individual study center prematurely for the following reasons:

- Lack of enrollment;
- Non-compliance with the requirements of the study protocol;
- Non-compliance with ICH-GCP and/or other applicable regulatory requirements.

### **3.7.3 Individual Patient**

If a patient discontinues the study treatment prematurely, the reason given must be fully evaluated and recorded appropriately in the source documents and the patient's eCRF. If the patient is discontinued from study treatment because of an AE, that AE should be indicated as the reason for discontinuation.

The Investigator can discontinue treatment of a patient at any time if medically necessary. In addition, patients meeting the patient discontinuation criteria must be discontinued from the study treatment.

Patients will be discontinued from the study treatment in the following circumstances:

- A patient who does not meet the enrolment criteria is inadvertently randomized, that patient must be discontinued from study treatment and the Sponsor or Clinical Research Organization (CRO) must be contacted.
- The Investigator decides that the patient should be discontinued from study treatment. If this decision is made because of an intolerable AE or a clinically significant laboratory value, the study drug is to be discontinued and appropriate measures are to be taken. The Sponsor or designee is to be notified immediately.
- Patient non-compliance, defined as refusal or inability to adhere to the study schedule or procedures (see Section 3.12).
- Treatment with a prohibited concomitant medication other than the use of appropriate medications for the treatment of AEs under the direction of the Sponsor and/or Investigator or Sub-investigator
- Lack of efficacy. Subjects who lack efficacy can be included in the PK and efficacy analysis. Patients receiving rescue therapy prior to Week 24 would not be eligible for second course of infusion.
- Patients who meet any of the following specific safety discontinuation criteria, however can be included for the PK analysis:
  - Patients who develop severe infusion-related reactions, especially severe dyspnea, bronchospasm or hypoxia, should have the infusion interrupted immediately to receive aggressive symptomatic treatment. In all patients, the infusion should not be restarted on the same day until complete resolution of all symptoms. At this time, the infusion may be initially resumed at the discretion of the Investigator at not more than one-half the previous rate. If the same ADRs occur for a second time, the infusion should be permanently discontinued.
  - Active TB
  - Invasive fungal infection or opportunistic infection including, but not limited to, listeriosis, legionellosis or pneumocystis.
  - Hepatitis B virus reactivation, in some cases resulting in fulminant hepatitis, or hepatic failure

- Any other AEs which, in the opinion of the Investigator or the Sponsor, could compromise the patient's safety or well-being if they continue to participate in the study.
- PML. Neurological warning signs include: major changes in vision, unusual eye movements; loss of balance or coordination; and disorientation or confusion
- Cancer: any malignant lesion. Patients with basal cell and squamous cell carcinomas of the skin or carcinoma in situ of the cervix uteri that has been excised and cured, may be continued on the study at the discretion of the Investigator.
- Pregnancy in a female participant
- Patient lost to follow-up despite reasonable efforts to make contact with the patient
- Patients who have a delay of >15 days in receiving the second infusion due to an AE or otherwise
- Judgment by the Investigator or Sub-investigator that study treatment discontinuation is necessary for reasons other than those described above.

To prevent missing data in important supportive efficacy and safety analysis, patients who discontinued study drug, will also attend all visits until week 52.

### **3.8 Screen Failures**

A screen failure patient is a patient who provided written informed consent (i.e., the patient signs an informed consent form [ICF]), but failed to meet all the inclusion criteria or who meets any of the exclusion criteria or withdraws consent prior to randomization. The reason for screen failure will be documented in the source documents.

Patients are only allowed to be re-screened once and it should be performed in consultation with the Sponsor or representative.

Laboratory tests if marginally abnormal may be repeated once at the discretion of the Investigator during the Screening period if the patient does not meet the criteria the first time. If the patient fails the laboratory criteria a second time, they will be considered a screen failure. Re-testing may only be done at the central laboratory except for ESR.

### **3.9 Re-screening**

Re-screening may be required if a patient has not met all the eligibility criteria. Patients are only allowed to be re-screened once and it should be performed in consultation with the

Sponsor or representative. Each patient must give written informed consent before re-screening occurs.

### **3.10 Definition of Completed Patients**

In this study, patients who complete at least the first course of study drug in Part A and undergo the tests and assessments at Week 52 will be defined as study completers.

### **3.11 Definition of Patients Lost to Follow-up**

Lost to follow-up is defined as a patient who stops attending study visits and study personnel are unable to contact the patient.

To prevent lost to follow-up, several approaches should be implemented to retain patients who fail to actively maintain contact with the investigator (e.g., telephone calls to friends or family members, emails, offers for transportation to the clinic, etc.).

If a patient is lost to follow-up, every possible effort must be made by the study center personnel to contact the patient and determine the reason for withdrawal. The measures taken to follow up must be documented.

### **3.12 Treatment Compliance**

The administration (dose, frequency and dates) of all concomitant medications (including new medications taken during the study and investigational product) should be recorded in the appropriate sections of the eCRF from Visit 1.

The infusion schedule consists of two 1,000 mg i.v. drug infusions of either SAIT101 or MabThera® or Rituxan® (the first on Day 1 and the second on Day 15) with the possibility of a further course of two 1,000 mg infusions (see Section 3.2.1). The study drugs will be administered at the study center. This should guarantee that full compliance was achieved, provided the patient attended the appropriate visits. Patients who miss the allocated day for the second of their two infusions will be contacted and another visit arranged as soon as practically possible in order to administer the missed dose of the study drug.

The prescribed dosage, timing, and mode of administration of the study drug may not be changed. Any departures from the intended regimen must be recorded in the eCRF.

Patients exhibiting poor compliance as assessed by attendance to appointments for their drug infusions should be counseled on the importance of good compliance to the study dosing regimen.

### **3.13 Protocol Deviations**

This study is intended to be conducted as described in this protocol. In the event of a significant deviation from the protocol due to an emergency, accident, or mistake (e.g., violation of the informed consent process, study drug dispensing or patient dosing error, treatment assignment error, patient enrolled in violation of eligibility criteria or concomitant medication criteria), the Investigator or Sub-investigator must contact the Sponsor at the earliest possible time. This will allow an early joint decision regarding the patient's continuation of study treatment. This decision will be documented by the Investigator and confirmed by the Sponsor.

## 4 RESTRICTIONS

### 4.1 Measures Regarding Patients Being Treated or Scheduled for Treatment at another Department or Hospital

When obtaining informed consent, the Investigator or Sub-investigator will confirm with the patient whether they are being treated or are scheduled for treatment at another department or hospital and note any drugs that they are using. If the patient is being treated by another physician (receiving treatment at another department or medical institution), the Investigator or Sub-investigator will contact the treating physician and inform them of the patient's participation in the study and provide information on the study drug. In addition to obtaining and recording the information on the medications prescribed at the other department or hospital, the appropriateness of the patient's study participation or continuation in the study will be decided.

### 4.2 Prohibited Medications/Therapies

Prior treatments required to be discontinued prior to Baseline is summarized in Table 4.

**Table 4 Prior Treatments Required to be Discontinued Prior to Baseline**

Treatment	Restriction
Leflunomide	Not permitted. Must be withdrawn at least 12 weeks prior to the beginning of the Treatment Period or a minimum of 4 weeks prior Day 1 if after 11 days of standard cholestyramine washout
Sulfasalazine	Not permitted within 4 weeks prior to Day 1
Hydroxychloroquine	Not permitted within 8 weeks prior to Day 1
Other non-biologic (conventional) DMARDs	Not permitted within 4 weeks prior to Day 1
Biologic DMARDs	Not permitted within defined washout period prior to Day 1 (see Table 6)

Treatment	Restriction
Intravenous or intramuscular corticosteroids	Not permitted within 6 weeks prior to Day 1
Intra-articular corticosteroids	Not permitted within 6 weeks prior to Day 1
Anti-infective agents	Intravenous anti-infective agents within 4 weeks prior to Screening or oral anti-infective agents within 2 weeks prior to Screening are not permitted
Live/attenuated vaccine	Not permitted within 6 weeks prior to Day 1 or during the study
Any drug that has not received regulatory approval for any indication	Not permitted within 4 weeks or a minimum of 5 half-lives, whichever is longer, prior to Day 1
Traditional herbal medicines (e.g., preparations containing derivatives of Tripterygium wilfordii Hook, Sinomenium acutum and Paeonia lactiflora )	Any traditional herbal medicine which has RA as an indication in its label is not permitted
Anti-cancer chemotherapy	Not permitted within 5 years prior to Screening
Surgical procedure	Not permitted within 4 weeks prior to Day 1
B cell modulating or B cell depletion therapies	Treatment with such therapies, such as, but not limited to rituximab, belimumab, atacicept, tabalumab, ocrelizumab, ofatumumab, obinutuzumab, epratuzumab and other experimental treatments is not permitted prior to or during the study

### 4.3 Concomitant Medications with Restrictions

Other medication that is considered necessary for the patient's safety and well-being (e.g., as a result of an AE) may be given at the discretion of the Investigator. Investigators are encouraged to discuss the introduction of any restricted medications with the Sponsor physician or representative. Any concomitant medications should be recorded in the appropriate sections of the eCRF.

The list of medications permitted during the study is presented in Table 5.

**Table 5 List of Medications Permitted During the Study**

Treatment	Restriction
Methotrexate	Patients must be taking MTX at a dose of 7.5-25 mg/week (oral or parenteral) throughout the study and for at least 12 weeks prior to study entry. Patients receiving a lower dose of MTX (<10 mg/week) should be doing so as a result of a documented evidence of intolerance to higher doses of MTX. The dose and route of administration should remain stable from 4 weeks prior to randomization and where possible, throughout the entire study period.
Folic or folinic acid	Patients must be taking oral folic or folinic acid or equivalent during the entire study (mandatory co-medication for MTX treatment), according to local standards and availability. The dosing regimen is at the Investigator's discretion.
Antipyretics	Patients will receive an antipyretic, e.g., paracetamol or equivalent, 30 to 60 minutes before each drug infusion.
Antihistamines	Patients will receive an antihistamine, e.g., diphenhydramine or equivalent, 30 to 60 minutes before each drug infusion.
Oral corticosteroids	If receiving current treatment with oral corticosteroids at the time of Screening ( $\leq 10$ mg/day prednisone or equivalent), the dose must remain stable during the 4 weeks prior to Day 1. Increases in corticosteroids for treatment of RA are not allowed over the study period and should be avoided (see Section 3.2.5). Reductions in the dose of corticosteroids will be allowed as clinically required only for safety reasons.
Intravenous or intramuscular corticosteroids	Use of i.v. or intramuscular corticosteroids for RA will be considered worsening of a patient's condition from Baseline and should be recorded as an AE in the eCRF. The only exception will be the administration of 100 mg i.v. methylprednisone or equivalent within 30 minutes before each infusion as part of the study procedures.
Intra-articular corticosteroids	Injection of intra-articular steroids during the study period is discouraged, but may be used in a limited fashion. Joints injected within 8 weeks prior to Week 24 and Week 52 will cause the exclusion of the joint from the subsequent efficacy analysis and therefore should be avoided. No more than 1 joint per 24-week period may be injected during the study period. No single injection should exceed 40 mg of triamcinolone (or equivalent) and the total dose of intra-articular corticosteroid may not exceed 80 mg of triamcinolone (or equivalent) during any 52-week period.
Inhaled/topical/ophthalmic steroids	Limited uses of these preparations are allowed during the study.
NSAIDs	Patients may be treated with NSAIDs, up to the maximum recommended dose, (including cyclooxygenase-2 inhibitors) throughout the study. The choice and doses of NSAIDs used to treat patients is at the discretion of the Investigator. Increases in the NSAID dose are not allowed over the study period and should be avoided. After Week 24, dose adjustments may be made only for safety reasons, and if absolutely required to treat disease flares, according to the Investigators' normal practices. Dose adjustments in NSAIDs cannot be made within 24 hours of a study visit. Aspirin may be taken to reduce cardiovascular risk, not to exceed 350 mg/day.

Treatment	Restriction
Analgesics (other than NSAIDs)	Analgesics up to the maximum recommended doses may be used for pain as required. However, patients should not take analgesics within 24 hours prior to a visit where clinical efficacy assessments are performed and recorded.
Non-pharmacological treatments (e.g., physical therapy)	Permitted freely.

Example washout periods for prior medications are presented in Table 6.

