#### **3.6.2.1.1 Joint Assessments**

Wherever possible, the same person should perform the joint assessment throughout the study (i.e., for all patients at each study center). Independent joint assessors (require at least one or more if necessary) will be assigned at each study center. This person will be independent to the rest of the study team in order to minimize any bias that could be introduced as a result of the assessment. Standardized training will be provided and the training records filed.

Each of the 66/68 joints will be evaluated for tenderness and swelling (prior to taking any required analgesic that day if possible). Immobilized or injected joints and prosthetic joints and joints which have undergone surgery within 1 year of the Screening visit will be excluded from the assessments.

The 66/68 Joint Count evaluates 66 joints for swelling and 68 joints for tenderness and pain with movement. Hip joints can be evaluated for tenderness only - but not for swelling.

The 66/68 joint count includes the following joints: the temporomandibular; sternoclavicular; acromioclavicular; shoulder; elbow; wrist; metacarpophalangeal, proximal interphalangeal, and distal interphalangeal joints of the hands; hip; knee; ankle; tarsus; and the metatarsal phalangeal and proximal joints of the feet.

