### 15.1. MAIN EFFICACY

#### 15.1.1. MAIN EFFICACY VARIABLE & DERIVATION

The main efficacy variable is the change from Baseline in DAS28-CRP at Week 24. The change from baseline in DAS28-CRP at Visit 24 will be calculated as follows:

Change at Visit 24= Value of DAS28-CRP at Visit 24 – Baseline value of DAS28-CRP

DAS28-CRP assessments consisted of tender joint counts (TJC), swollen joint counts (SJC) and C-reactive Protein (CRP). Formula is listed as follow or a calculator is available online at the following website: <http://www.das-score.nl/das28/DAScalculators/dascalculators.html>.

- $DAS28-CRP = [0.56 \times \sqrt{(TJC28)} + 0.28 \times \sqrt{(SJC28)} + 0.36 \times \ln(CRP+1)] \times 1.10 + 1.15$

TJC28: Tender Joint Count (28 joints); SJC28: Swollen Joint Count (28 joints); CRP(mg/L).

28 joints include proximal interphalangeal joints (10 joints), metacarpophalangeal joints (10 joints), wrists (2 joints), elbows (2 joints), shoulders (2 joints) and knees (2 joints).

DAS28-CRP will be considered missing if any of the three components is missing.

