#### 15.1.2. MISSING DATA AND OUTLIER METHODS FOR MAIN EFFICACY VARIABLE

All analyses of main efficacy variables will be based on available data. No missing data will be imputed and no outlier will be excluded.

For the sensitive analysis to main efficacy analysis, missing data for DAS28-CRP prior to Week 24 will be imputed and outlier will be handled as described in Section 15.1.4.

If there is any doubt of outlier, a box plot will be used for detecting potential outliers among all subjects, i.e. values higher than  $Q3+1.5 \times IQR$  or lower than  $Q1-1.5 \times IQR$  ( $Q1=25^{th}$  quartile,  $Q3=75^{th}$  quartile,  $IQR=Q3-Q1$ ). The potential outliers among all subjects will be reviewed by medical and be confirmed during blinded data review meeting and prior to database lock and unblinding. If there are any confirmed outliers, then analysis will be performed with and without the outlier(s) to see how the outliers affect study results as sensitivity analysis after unblinding. If there is no confirmed outlier, then box plot and the sensitivity analysis will not be performed after unblinding for final analysis.

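### Injected joints leave the later joint counts, but the SAP has no rule for them: read literally, a joint active at baseline and still active lowers DAS28-CRP and can tip an ACR joint item

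*Protocol*

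**What the plan says.** Protocol Table 5 discourages intra-articular steroids but permits them within limits. "No more than 1 joint per 24-week period may be injected during the study period". On the consequence for analysis it says: "Joints injected within 8 weeks prior to Week 24 and Week 52 will cause the exclusion of the joint from the subsequent efficacy analysis".

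Protocol 3.6.2.1.1 has its own rule on what the joint assessor leaves out: "Immobilized or injected joints and prosthetic joints and joints which have undergone surgery within 1 year of the Screening visit will be excluded". It mentions no 8-week window.

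SAP 15.1.1 builds DAS28-CRP from raw 28-joint tender and swollen counts plus CRP, and defines the change as "Value of DAS28-CRP at Visit 24 – Baseline value of DAS28-CRP". SAP 15.2.1 defines the ACR joint items as percent change between the raw visit count and the raw baseline count. On incomplete data, SAP 15.1.1 says "DAS28-CRP will be considered missing if any of the three components is missing", and SAP 15.1.2 adds "No missing data will be imputed and no outlier will be excluded" for the main analysis.

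The SAP does not remove an excluded joint from baseline, prorate the count, carry the joint's status forward or score it as active. It also does not say whether a count lacking one joint is a missing component. The sensitivity analyses in SAP 15.1.4 cover outliers, added covariates, a treatment interaction and missing Week 24 data, but not injected joints.

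**The concern.** A count from which a joint has been dropped is lower by one if that joint was still tender or swollen. When it is subtracted from a baseline count that includes the joint, the drop reads as improvement. The patients affected are those who needed extra local treatment, so the direction is unwelcome. Table 5 itself treats i.v. or intramuscular steroid given for RA as a worsening, whereas a local injection could register as a gain.

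The counts feed the main efficacy variable, ACR20/50/70, the EULAR categories (cut-points 0.6 and 1.2) and SDAI remission. The Week 24 counts also decide eligibility for the second course.

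The two protocol passages can give different counts for one patient. Take a joint injected at Week 10, which is 14 weeks before Week 24. Table 5 keeps it in the Week 24 analysis, while 3.6.2.1.1, read as it stands, does not.

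**Working it through.** **Inputs.** The DAS28-CRP formula is from SAP 15.1.1 and the ACR formula from SAP 15.2.1. The margin of ±0.6, SD of 1.0, one-sided 2.5% level and 94 (FAS) or 77 (PP) patients per group are from Protocol 6.1. Injection rates by arm are not given; between-arm differences of 5 to 20 percentage points are assumed.

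**1. The plan's own power.** With SE = SD × √(2/n) and no true difference, power = 2Φ(0.6/SE − 1.96) − 1.
- n = 94: SE = 0.146, power 96.9% (t-based 96.7%); stated 96%.
- n = 77: SE = 0.161, power 92.2% (t-based 91.8%); stated 91%.

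The stated figures are reproduced closely enough to serve as the reference.

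**2. Effect on one score.** DAS28-CRP = [0.56√TJC28 + 0.28√SJC28 + 0.36 ln(CRP+1)] × 1.10 + 1.15. With equal counts k, dropping one joint that is both tender and swollen lowers the score by (0.616 + 0.308) × (√k − √(k−1)) = 0.924 × (√k − √(k−1)).

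| Active joints at visit | Fall in DAS28-CRP |
|---|---|
| 15 to 14 | 0.12 |
| 10 to 9 | 0.15 |
| 6 to 5 | 0.20 |
| 4 to 3 | 0.25 |
| 2 to 1 | 0.38 |
| 1 to 0 | 0.92 |

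**3. One patient, different results.** Illustrative baseline: 12 tender, 10 swollen, CRP 15. Week 24: 6 tender, 6 swollen, CRP 10.
- Joint kept at both times: change −0.993.
- Joint dropped at Week 24 only: −1.190.
- Joint dropped at both times: −1.049.
- If the reduced count is treated as missing: no score, and no imputation in the main analysis.

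**4. ACR joint item.**
- Baseline 10, 9 active at the visit: (9−10)/10 = −10%, not met. Dropped at the visit only: (8−10)/10 = −20%, met. Dropped at both: (8−9)/9 = −11%, not met. This flip depends on the unadjusted baseline.
- Baseline 6, 5 active: (5−6)/6 = −16.7%, not met. Dropped at the visit only: (4−6)/6 = −33%, met. Dropped at both: (4−5)/5 = −20%, also met. This case does not isolate the baseline problem.

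ACR20 still needs both joint counts and three of five other items.

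**5. Effect on the arm contrast.** Shift = difference in injection rate × fall per affected patient.
- 5% × 0.2 = 0.01; FAS power 96.8%.
- 10% × 0.4 = 0.04; 96.2%.
- 20% × 0.4 = 0.08; 94.2%.
- Extreme, 20% × 0.92 = 0.18; 81.4%. This needs every affected patient to have a single active joint left.

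With equal rates and equal shifts in the two arms, the contrast does not move.

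**The case against.** The strongest reply is that no document says the joint stays in the baseline count. Table 5 excludes it from the efficacy analysis, and that analysis is a change from baseline, so removal at both times is a possible reading. Treating the count as missing is another. This stands: retention at baseline is an inference from the word subsequent in Table 5 combined with unadjusted SAP formulas. It is the literal result of those texts, but not a stated intention.

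The mechanism also needs several conditions, and these stand too. The joint must be active at baseline and still active at the visit. If the injection worked, the count is the same either way; if the joint was quiet at baseline, exclusion hides a worsening but scores no improvement. DAS28-CRP is touched only when the joint is one of the 28. Injection is discouraged and capped at one joint per 24 weeks.

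The sentence in 3.6.2.1.1 could be read as a list fixed around Screening, because its last item is. That makes its lack of a window arguable, but the passages still need aligning.

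Requiring equivalence in both FAS and PP is a weaker safeguard than it looks. SAP 4.5 allows PP exclusion for other situations affecting efficacy assessments, but a permitted injection is not plainly one of them.

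A reader might infer that the plan conceals a difference between the products. The documents do not support this. They give no injection rates, the trial is double-blind, and the contrast moves only by the between-arm difference. Nor should a single-patient fall of 0.92 be set against 0.6, which is a margin for a difference in means.

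**Conclusion.** The point holds as a gap in the derivation that, followed literally, gives a biased count for some patients. The size for an affected patient is about 0.12 to 0.20 DAS28-CRP units at 15 to 6 active joints, and up to 0.92 when one active joint remains. ACR joint items can change only at a boundary. For the mean contrast, 0.01 to 0.08 is the likely order, resting on assumed rate differences of 5 to 20 points and falls of 0.2 to 0.4 per patient; all of those injected are taken to meet the conditions above, so the range is generous. The equivalence conclusion is not seriously threatened. The change is still worth making, because the rule touches the main efficacy variable and the choice would otherwise be made during programming.

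**What to change.** Before unblinding:
- In SAP 15.1.1 and 15.2.1, state that within the exclusion window an injected joint is counted at its last pre-injection status, or as tender and swollen if it was injected for a flare after the last scheduled count. The second clause is needed because the last scheduled count is Week 16 for the Week 24 window and Week 36 for the Week 52 window. Plain carry-forward would score a joint that was quiet then and flared later as quiet.
- Add a sensitivity analysis that removes the joint at both baseline and the visit.
- Reconcile Protocol 3.6.2.1.1 and Table 5 to one exclusion period.
- Report injections by arm, with timing and whether the joint is among the 28.

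The cost is a few sentences and one derivation step, since each of the 66/68 joints is evaluated individually. The documents do not say whether the injected joint and the reason for injection are recorded, so this should be confirmed first. The downside is that a joint that would have improved anyway is scored conservatively.
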